2.0 Specific Aims

Specific Aim 1: To determine whether Gabapentin used as a preventive measure during chemoradiation can reduce radiation-induced mucositis associated pain in head and neck cancer patients as measured by: 1) pain scores on the Vanderbilt Head and Neck Symptom Survey (VHNSS version 2.), and 2) analgesic use.

Hypothesis 1.1: Compared to controls, patients using Gabapentin during radiation-based therapy will have a 1.5 point decreases in self-reported oropharyngeal pain (on a scale of 0 to 10) week six of radiation.

Hypothesis 1.2: Compared to controls, patients using Gabapentin during radiation-based therapy will have a 20% decrease in opioid use (as measured in morphine equivalents) at week six of radiation.

Specific Aim 2: To determine whether pain control is associated with weight loss (in pounds) and duration of use of percutaneous endoscopic gastrostomy utilization (in days).

Hypothesis 2.1 Patients with less pain will have decrease weight loss.

Hypothesis 2.2 Patients with less pain will have a shorter duration of PEG placement.

Specific Aim 3: To assess the safety (grade 3 or 4 adverse events) and tolerability of using gabapentin (discontinuation of drug due to side effects - yes or no).

Specific Aim 4: To correlate pain severity with frequency and severity of general systemic symptoms.

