Prior to initiating therapy, patients will undergo education sessions with study staff. The educational intervention will include a discussion of oral health foundations as well as a discussion of pain management. This education is standardly applied to all VUMC patients undergoing radiation therapy for HNC and will not be otherwise documented. In addition, patients will also be given written material to review. Patient will be given a pain diary and instructed on its use. Baseline pain medication use will be documented. Patients will complete the demographic survey. Patients randomized to gabapentin will be given a prescription for gabapentin with dose escalation as noted in the treatment section. Patients who do not have insurance or who are unable to afford gabapentin will be provided with medication from the indigent pharmacy. All baseline assessments must be done within 4 weeks of starting concurrent chemoradiation.

Weekly On Treatment Visits:

Starting with the initiation of concurrent chemoradiation, patients will be evaluated on a weekly basis. The evaluation will include:

- 1) review of the weekly pain survey
- 2) for patients on gabapentin (Arm 2) --we will review their compliance log and identify any barriers to compliance and strategies to improve their compliance
- 3) adjustment of pain regimen
- 4) completion and review of the Vanderbilt head and neck symptom survey
- 5) mucositis grading.

End-of-Treatment Visit:

Patients will undergo an evaluation at their final radiotherapy visit or within 2 weeks after. This will include the following:

- 1) review of the monthly diary survey
- 2) for patients on gabapentin (Arm 2) --we will review their compliance log and identify any barriers to compliance and strategies to improve their compliance

- 3) adjustment of pain regimen
- 4) completion and review of the Vanderbilt head and neck symptom survey
- 5) mucositis grading.

6.0 Study Measures:

6.1 Mucositis Grading:

Patients will have an oral exam twice a week as part of standard of care. Mucositis will be graded based on the World Health Organization criteria. Mucositis assessments will be done by trained study staff.

6.2 Patient Reported Outcome Measures:

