Study Visit: The study nurse will meet with the patient at baseline, weekly during radiation therapy, and at 1, 2 and 3 months post-treatment. At each study visit the study nurse will 1) administer appropriate questionnaires, 2) review the patient's pain diary and compliance diary, 3) document concurrent medications, 4) document toxicities based on CT CAE criteria 4.0, 5) identify and prepare reports for any adverse events, 6) document any dose adjustments in pain medications as recommended by the physician or nurse practitioner, and 7) educate the patient regarding medication dose and schedule.

As these patient reported outcome measures represent outcomes of interest for the study, they will not be altered by study staff due to missingness as changes would threaten the validity of the tool.

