Appendix I: Studies to be Done:

	Baseline¥	Week 1	Week 2	Week 3	Week 4	Week 5	Week 6 *	Week 7 *	1,2 3 Months post tx
Study Visit	X	X	X	X	X	X	X	X	X
Chemoradiation Teaching	X								
Foundations of Oral Care	X								
Foundations of Pain Management	X								
Randomization	X								
Gabapentin Arm 2 Only		X	X	X	X	X	X	X	X
Mucositis Grading	X	X	X	X	X	X	X	X	X
Demographic Survey	X								
VHNS Version 2.0		X	X	X	X	X	X	X	X
Pain Survey		X	X	X	X	X	X	X	X
Compliance Survey Arm 2 Only		X	X	X	X	X	X	X	X
Neurotoxicity Scale	X						X		X (month 3 only)
POMS	X						X		X (month 3 only)
QOL	X						X		X (month 3 only)

Disease and Treatment Form	X								
----------------------------	---	--	--	--	--	--	--	--	--

‡ All baseline assessments must be done within 4 weeks before starting concurrent chemoradiation.

* Weekly assessments will continue until the completion of chemoradiation which may vary between 5 and 7 weeks.

An End of Treatment Visit will be conducted 2 weeks after Chemoradiation therapy

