10.0 Statistical Considerations and Sample Size Justification

General evaluation and analysis plan: Statistical software will be used to summarize the data collected and to test study hypotheses. Intent-to-treat principles will be used for all analyses. An interim analysis of the VHNSS pain scores will be conducted when 50% of the participants have been randomized and have completed the 3 month follow-up period. To maintain the final overall alpha of $P < 0.05$, the Haybittle-Peto approach will be used: the trial will be stopped at that point if the symmetric stopping boundaries of $P < 0.001$ are met. The interim analysis will only be used for this purpose, i.e. no futility analyses will be conducted.

Management of Missing Data: In-depth investigations of patterns of missing data will be undertaken. Given the longitudinal nature of this study, we expect two types of missing data: 1) randomly missing responses to items within the self-report measures (e.g., VHNSS) and 2) non-randomly missing lost-to-follow up (LTF) assessments. Our proposed sample size accommodates up to 30 LTF (i.e., up to 20% of those randomized) to arrive at a total analysis sample size of 120. Randomly missing item response data will be handled via protocols specified by the instrument developers. When there is no specified protocol, if the participant has completed 75% or more of the items on a particular instrument, prorated scores for that instrument will be generated using available item responses. Non-randomly missing data will be assessed to determine whether it provides clinically important information and implications for generalizability of findings. All efforts as outlined by White et al. (2011) for handling missing outcome data in an RCT-ITT analysis will be conducted.

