Analyses for study aims. Graphical and descriptive statistical summaries will be generated for all study variables. Evaluation of the key outcome variable data distributions (VHNSS mouth pain scores, opioid dose) will inform the required test distribution (e.g., normal, log-normal). Mixed-level general linear modeling will be used to test study hypotheses. Given that patients will have varying VHNSS pain scores prior to beginning radiation, those baseline values will be included as a covariate in the analyses of outcomes [EOT: VHNSS pain scores (H1.1); opioid use (H1.2); weight loss (H2.1); duration of PEG (H2.2); general symptoms (Aim 4)]. Frequency distributions will summarize the safety and tolerability outcomes (Aim 3). All tests of statistical significance will maintain maximum Type I error of 0.05 ($p < 0.05$).

Sample size justification. The proposed sample size was based on typical VHNSS pain score values during/end-of-treatment in prior studies (M=4.5, SD=2.8). A total sample size of 120 patients (60 per arm) who complete the protocol will provide 80% statistical power (2-tailed alpha=0.05) to detect a decrease of 1.5 points on the VHNSS pain scale due to the addition of gabapentin to usual care. Given a change of 2.0 points on the scale is proposed to be clinically meaningful, this slightly larger sample size will provide coverage in the case that our sample values are slightly more variable than those observed in our prior studies. A total sample size of 120 will also enable us to detect correlations as small 0.25(6.3% shared variance) with 80% power and 2-tailed alpha=0.05. We expect clinically meaningful associations to be larger than this value.

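### Hypothesis 1.1 is set at week six of radiation in the aims but listed at end of treatment in the analysis plan, and the interim stopping rule names no time point

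*Combined protocol and SAP*

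**What the plan says.** - **Aims (2.0).** Hypothesis 1.1 predicts, against controls, "a 1.5 point decreases in self-reported oropharyngeal pain (on a scale of 0 to 10) week six of radiation". Hypothesis 1.2, on opioid use, is also set at week six.
- **Analyses (10.0).** The sentence on the baseline covariate lists the outcomes as "EOT: VHNSS pain scores (H1.1); opioid use (H1.2); weight loss (H2.1); duration of PEG (H2.2); general symptoms (Aim 4". Week six is not mentioned. The abbreviation is not spelled out, and it is unclear whether it covers only the first item or the whole list. The model is a mixed-level general linear model with no contrast named.
- **Sample size (10.0).** "The proposed sample size was based on typical VHNSS pain score values during/end-of-treatment in prior studies", with mean 4.5 and SD 2.8. The target difference is the 1.5 points of H1.1.
- **Interim (10.0).** "An interim analysis of the VHNSS pain scores will be conducted when 50% of the participants have been randomized" and have finished three months of follow-up. The trial stops if P < 0.001. This fixes the data cut, but not the assessment to be tested.
- **Course length (Appendix I, both copies).** "Weekly assessments will continue until the completion of chemoradiation which may vary between 5 and 7 weeks".
- **End-of-treatment timing.** Section 5.6: "Patients will undergo an evaluation at their final radiotherapy visit or within 2 weeks after". The footnote to the first copy of Appendix I: "An End of Treatment Visit will be conducted 2 weeks after Chemoradiation therapy". The second copy has no such footnote.
- **Visit list (6.2).** "The study nurse will meet with the patient at baseline, weekly during radiation therapy, and at 1, 2 and 3 months post-treatment". No end-of-treatment visit is listed separately.

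**The concern.** The documents label no endpoint as primary, but H1.1 sets the sample size and VHNSS pain is the only outcome that can stop the trial early. That comparison should have one definition. As written, the aims point to week six, the analysis section points to EOT, and no passage equates the two or ranks them. Someone who has seen the results could report whichever comparison looks better as the test of H1.1, and both choices would follow the plan. The interim rule is looser still, because several VHNSS assessments will exist for each patient by then and none is named. Section 1.4 criticises the earlier retrospective study partly because its outcomes were not fixed in advance. This leaves a similar gap in the trial's key test.

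**Working it through.** **1. Are week six and EOT the same measurement?**

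- A 5-week course ends before week six, and weekly assessments stop at completion. Such a patient has no scheduled on-treatment week-six score.
- A 6-week course can have week six and the final radiotherapy visit coincide.
- A 7-week course has a week-six score, and EOT comes later.
- The earliest EOT is a 5-week course seen at the final visit: week 5. The latest is a 7-week course seen two weeks after: 7 + 2 = week 9.
- Section 1.2 says pain is worst at completion of therapy, and 5.2 says mucositis then resolves over 1 to 3 months. Moving the visit therefore moves it along a changing curve.

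They coincide for some patients and differ for others.

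**2. What could the interim test use?** VHNSS occasions by the data cut: weeks 1 to 7 (up to 7), EOT (1), months 1 to 3 (3), so up to 11. A test at any one of them, or across all, fits the text.

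**3. Does the sample size settle the time point?** Standardised difference 1.5/2.8 = 0.536.

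- Normal formula: n per arm = 2 × [2.8 × (1.960 + 0.842)/1.5]² = 54.7, so 55. The t-test needs 56.
- At the planned 60 per arm, t-test power is 82.9% (normal approximation 83.5%), against the stated 80%. The excess is conservative and matches the stated cushion for variability: 60 per arm gives 80% at an SD of about 2.91.
- Loss to follow-up: 120/(1 − 0.20) = 150, as stated.

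The calculation uses one difference and one SD described as during or at the end of treatment. It fits either time point.

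**4. Illustration: type I error if significance at either time point were claimed.** The correlation ρ between the two test statistics is assumed, because the documents give none. Error = 1 − P(|Z₁| ≤ c and |Z₂| ≤ c), bivariate normal.

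| ρ | Nominal 0.05 | Nominal 0.001 (interim) |
|---|---|---|
| 0.5 | 9.07% | 0.196% |
| 0.8 | 7.81% | 0.176% |
| 0.95 | 6.46% | 0.143% |

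**5. Illustration: how often the choice would matter.** Suppose the true effect is 1.5 points with SD 2.8 at both times. Each statistic then has mean 1.5/[2.8 × √(2/60)] = 2.93, and the tests disagree with probability 2 × [P(Z₁ > 1.96) − P(both > 1.96)]. That is about 20% of trials at ρ = 0.5, 12.5% at 0.8 and 6% at 0.95.

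**6. Illustration: power of a week-six test when some courses last 5 weeks.** The shares are assumed: 10% leaves 54 per arm with a week-six score, 20% leaves 48. The mixed model keeps the other patients' week-5 scores, with week 5 to week 6 correlation r and no baseline covariate: effective n = 1/[(1 − r²)/n₁ + r²/60].

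| n₁ per arm | Complete-case t-test | Effective n, r = 0.5 to 0.8 | Mixed-model power |
|---|---|---|---|
| 54 | 78.8% | 55.4 to 57.7 | 79.8% to 81.4% |
| 48 | 73.8% | 50.5 to 55.0 | 76.0% to 79.5% |

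Simulation with 20,000 trials per setting gave 79.6% and 81.4% for 54, and 75.4% and 79.5% for 48. The reference is 82.9% with no week-six scores missing.

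**The case against.** The best defence is that week six may simply be a nominal label for the end of treatment. It is the middle of the 5-to-7-week range and the only on-treatment week with the neurotoxicity, mood and quality-of-life scales. EOT appears once, undefined, in a sentence about covariates, and the same list includes PEG duration, which fits an end-of-treatment reading poorly. This shows that the meaning of EOT is an inference, though the natural one. It does not reconcile the passages, because none says that week six means end of treatment.

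The week 5 to week 9 span mixes course length with the visit window. That is fair: for one patient the window is 0 to 2 weeks after the last radiotherapy visit, and the Appendix I timing lies inside it. A visit held on the last radiotherapy day is arguably covered by the weekly visits in 6.2. Both points make the window a secondary matter, but the span and the gap in the list are still literally as stated.

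The numbers are open to criticism too. No passage permits claiming either test, and 10.0 caps type I error at 0.05. The interim inflation is trivial in absolute terms. The power figures concern missing week-six scores, the complete-case test is not the planned analysis, and at 10% short courses the mixed model stays close to 80%. A 5-week patient's EOT visit may also fall near week six. All of this stands, so the figures are illustrations and the finding rests on the text.

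**Conclusion.** The concern holds. The hypothesis that sizes the trial has two time points in the plan, and the interim rule built on the same scale has none. This is a contradiction and not merely missing detail, and it must be resolved before comparative data are seen. It rests on one inference, that EOT means the End-of-Treatment Visit. Whether that label also reaches H1.2 remains unclear.

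The size depends on assumed inputs: type I error of 6.5% to 9.1% if either test could be claimed (0.14% to 0.20% at the interim boundary), and disagreement between the tests in about 6% to 20% of trials under the planned effect. The power cost of choosing week six depends on the share of 5-week courses, which the documents do not give, and is small if that share is near 10% and the mixed model is used.

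**What to change.** Before any comparative data are seen, including the interim, name H1.1 as the primary test with one time point and one model contrast, and write it identically in 2.0, in 10.0 and in the interim rule. Either option works:

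- **(a) End of treatment.** Define EOT in 10.0, give one visit window in the same words in 5.6 and both copies of Appendix I, and add the visit to the list in 6.2.
- **(b) Week six.** Test the week-six contrast of the mixed model fitted to all weekly scores, with a stated rule for patients whose course ends earlier. For example, they contribute their on-treatment scores and no post-treatment score is substituted.

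The choice between them is the investigators'. Report the other time point as secondary, and state the time point for H1.2.

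The cost is protocol wording only. There are no extra visits, questionnaires or patients, and the planned 120 completers (150 randomised) are unchanged.

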|--|-------|---|---|---|---|---|---|---|---|---|--------|
| | 0 | 1 | 2 | 3 | 4 | 5 | 6 | 7 | 8 | 9 | 10 |
| | Never | | | | | | | | | | Severe |

General Symptom Subscale:

- 51. I have unexplained fatigue**

- | | | | | | | | | | | | |
|------------|--|---|---|---|---|---|---|---|---|---|------------|
| | 0 | 1 | 2 | 3 | 4 | 5 | 6 | 7 | 8 | 9 | 10 |
| | Never | | | | | | | | | | Always |
| 52. | Fatigue limits my day to day activity | | | | | | | | | | |
| | 0 | 1 | 2 | 3 | 4 | 5 | 6 | 7 | 8 | 9 | 10 |
| | Never | | | | | | | | | | Always |
| 53. | I have problems falling asleep | | | | | | | | | | |
| | 0 | 1 | 2 | 3 | 4 | 5 | 6 | 7 | 8 | 9 | 10 |
| | Never | | | | | | | | | | Always |
| 54. | I have problems staying asleep | | | | | | | | | | |
| | 0 | 1 | 2 | 3 | 4 | 5 | 6 | 7 | 8 | 9 | 10 |
| | Never | | | | | | | | | | Always |
| 55. | I have episodes of unexplained sweating | | | | | | | | | | |
| | 0 | 1 | 2 | 3 | 4 | 5 | 6 | 7 | 8 | 9 | 10 |
| | Never | | | | | | | | | | Frequently |
| 56. | There are times when I am cold and others around me are not | | | | | | | | | | |
| | 0 | 1 | 2 | 3 | 4 | 5 | 6 | 7 | 8 | 9 | 10 |
| | Never | | | | | | | | | | Always |
| 57. | There are times when I am hot and others around me are not | | | | | | | | | | |
| | 0 | 1 | 2 | 3 | 4 | 5 | 6 | 7 | 8 | 9 | 10 |
| | Never | | | | | | | | | | Always |
| 58. | I have trouble with my memory or processing my thoughts | | | | | | | | | | |
| | 0 | 1 | 2 | 3 | 4 | 5 | 6 | 7 | 8 | 9 | 10 |
| | Never | | | | | | | | | | Always |
| 59. | I have joint pain or muscle aches other than in my neck and shoulders | | | | | | | | | | |
| | 0 | 1 | 2 | 3 | 4 | 5 | 6 | 7 | 8 | 9 | 10 |
| | Never | | | | | | | | | | Always |
| 60. | I feel sad or depressed | | | | | | | | | | |
| | 0 | 1 | 2 | 3 | 4 | 5 | 6 | 7 | 8 | 9 | 10 |

Never

Always

61. I feel anxious

0 1 2 3 4 5 6 7 8 9 10
Never Always

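### Aim 4, as most naturally read, is one between-patient association at end of treatment; the weekly paired scores that could separate within-patient from between-patient association have no planned use

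*Combined protocol and SAP*

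**What the plan says.** - **The aim.** Section 2.0, Specific Aim 4: "To correlate pain severity with frequency and severity of general systemic symptoms". It names no instrument, time point, coefficient or level of inference (within or between patients), and it has no numbered hypothesis.
- **The analysis.** Section 10.0, Analyses for study aims, states: "Mixed-level general linear modeling will be used to test study hypotheses". It then says that baseline VHNSS pain enters as covariate: "those baseline values will be included as a covariate in the analyses of outcomes [EOT: VHNSS pain scores (H1.1); opioid use (H1.2); weight loss (H2.1". The same bracketed list ends with "general symptoms (Aim 4". No random effect, time term or treatment arm is specified for Aim 4, and the baseline general symptom score is not adjusted for.
- **The sizing.** Section 10.0, Sample size justification, says that 120 patients suffice to "detect correlations as small 0.25(6.3% shared variance) with 80% power and 2-tailed alpha=0.05". It adds that clinically meaningful associations are expected to be larger.
- **The instrument.** In Appendix B the pain items (22-28) and the General Symptom Subscale (items 51-61) are on one patient-completed form. Item 28 asks whether pain disturbs sleep; item 54 is "I have problems staying asleep". Item 59, in the general subscale, asks about joint pain and muscle aches.
- **The schedule.** Section 5.6 and both Appendix I calendars have the VHNSS completed at each weekly on-treatment visit (5 to 7 weeks) and again at 1, 2 and 3 months. Neither calendar marks it at baseline.

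**The concern.** With one value per patient, a correlation between pain and general symptoms mixes two things. One is the extent to which a patient's general symptoms rise and fall with that patient's pain. The other is the extent to which patients who score high on one part of the form score high on the other, through reporting style, persistent low mood or more intensive treatment. A single time point cannot tell them apart.

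Two features of this trial sharpen the point. Both scores come from the same form, completed at the same time, with some shared content. Arm may also matter: section 7.0 lists fatigue (11%), drowsiness (19%-21%, immediate release), depression (2%) and amnesia (2%) for gabapentin, which resemble items 51-52, 58 and 60. If gabapentin lowered pain and raised these symptoms, a correlation pooled over arms would be distorted.

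What is at stake is how informative the answer to a stated specific aim is, when the data for a better answer are already scheduled.

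**Working it through.** **1. The plan's own figure.** Inputs from section 10.0: N = 120, r = 0.25, two-sided alpha 0.05.
- Noncentral t with df = 118: ncp = r√N/√(1−r²) = 0.25 × √120/√0.9375 = 2.83; critical t = 1.980; power = 0.801. The smallest N that gives 80% is 120.
- Fisher z: atanh(0.25) × √117 − 1.960 = 0.803, power 0.789.
- 0.25² = 6.25%, given as 6.3%.

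The figure reproduces.

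**2. What stable differences alone can produce.** Assumption, not in the documents: there is no within-patient link, and a stable factor common to both scores explains a share s of the variance of each. Then r = s. Equivalently, r = ICC × (correlation of the stable parts), where ICC is the stable share of a score's variance; ICC 0.5 with 0.5 gives 0.25.

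**3. The planned covariate.** Let x be the correlation of EOT pain with general symptoms, y that of baseline pain with general symptoms, and c that of baseline with EOT pain. The partial correlation is (x − c·y)/√[(1−c²)(1−y²)].
- Case A: the shared factor is the only stable part of pain, and baseline pain carries it. Then y = x = c = s, and the result simplifies to s/(1+s).
- Case B: pain also has a stable part of its own worth 25% of its variance (assumed). Then y = x = s and c = s + 0.25.

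Chance of p < 0.05 by Fisher z at N = 120 (√117 unadjusted, √116 with one covariate):

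| s | Unadjusted r | p < 0.05 | Case A r | p < 0.05 | Case B r | p < 0.05 |
|---|---|---|---|---|---|---|
| 0.15 | 0.15 | 37% | 0.130 | 29% | 0.099 | 19% |
| 0.20 | 0.20 | 59% | 0.167 | 44% | 0.126 | 27.5% |
| 0.25 | 0.25 | 79% | 0.200 | 59% | 0.149 | 37% |

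Simulation agrees: 36%, 59% and 79% unadjusted (4,000 runs per scenario); 30%, 43% and 60% in case A and 18%, 29% and 36% in case B (3,000 runs).

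**4. Sensitivity to the assumptions.** With ICC from 0.3 to 0.7 and stable parts correlated 0.3 to 0.7, unadjusted r runs from 0.09 to 0.49. Adjusted for a baseline pain score that carries the same stable part, it runs from 0.07 to 0.24. If baseline pain is only weakly related to EOT pain (c = 0.1 to 0.3, y = x·c/ICC), adjustment removes little: with ICC 0.5 and 0.5, r stays at 0.22 to 0.25.

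**5. What the weekly pairs offer.** Centring each patient's scores on that patient's mean leaves df = 120(k−1) − 1 for k weeks. The smallest detectable within-patient r at 80% power is tanh[(1.960 + 0.842)/√(df−1)]:
- 5 weeks: df = 479, r = 0.127
- 6 weeks: df = 599, r = 0.114
- 7 weeks: df = 719, r = 0.104

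These assume complete data and independent weekly residuals. In simulation with stable differences only (3,000 runs, 6 weeks), the within-patient estimate averaged 0.00 and was significant in 4% to 5% of runs.

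**The case against.** The strongest reply is that Aim 4 asks only for an association. It has no hypothesis and makes no causal claim, and the neighbouring Aim 2 hypotheses are plainly comparisons between patients. A between-patient correlation answers the aim as written. This stands, and it rules out several stronger readings that a reader might infer:

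- **That the percentages in the table are false-positive rates.** They are not. In those scenarios a between-patient association does exist; what is absent is a within-patient one. The shares are assumed, and r follows directly from them.
- **That stable differences would reproduce the correlation the plan is looking for.** The plan gives 0.25 as a detectable minimum and expects meaningful associations to be larger.
- **That the plan commits itself to a single time point.** The EOT label is the natural reading but is not conclusive. Section 10.0 also names mixed-level modelling, Hypotheses 1.1 and 1.2 specify week six, and duration of PEG use, in the same list, need not be complete at end of treatment.
- **That the within-patient coefficient alone is the right answer.** It removes stable differences only. Mood and opioid dose can change from week to week, and section 5.6 provides for weekly adjustment of the pain regimen. If a week-specific factor is assumed to explain 10% or 15% of the weekly variance of both scores, the within-patient test is significant in 68% or 95% of simulated trials (120 patients, 6 weeks) without any causal link.
- **That the pain score certainly overlaps the sleep items.** Section 10.0 refers to mouth pain and does not list the items, so item 28 may not be part of the score. Changing to items 25-26 would not help: they name no pain site, and item 59 in the general subscale is itself a pain item.

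What survives is narrower: the level of inference is unstated, and the data that would inform it have no planned use for this aim.

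**Conclusion.** The point holds as a worthwhile improvement, not as an error. No stated figure is wrong, and the EOT association is valid for what it is. It cannot tell symptoms that follow pain from patients who score high throughout. Under assumed stable shares of 15% to 25%, stable differences alone give r of 0.15 to 0.25, and less once baseline pain is adjusted for: about 0.13 to 0.20 in case A and 0.10 to 0.15 in case B. How much less depends on how strongly baseline pain predicts EOT pain, which the documents do not give.

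That adjustment also needs a measurement that neither Appendix I calendar schedules, although section 1.6 implies a VHNSS before chemoradiation. A reader might infer that a significant result would show pain driving systemic symptoms; the documents make no such claim, and neither the planned analysis nor the one proposed here could support it.

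**What to change.** 1. **State the instrument, time points and level of inference for Aim 4.** The General Symptom Subscale is the natural instrument, but the aim does not name it.
2. **Fit one mixed model to all weekly on-treatment pairs.** Outcome: general symptom score. Predictors: the patient's mean pain, the weekly deviation from that mean, week and arm, with a random patient intercept. The week term matters because section 1.2 expects pain to build up over treatment in most patients, and a common time course should not count as a within-patient link.
3. **Report the between-patient and within-patient coefficients side by side.** Interpret both as associations, and name time-varying confounding, such as opioid changes, as a limitation of the second.
4. **Keep the plan's VHNSS mouth pain score as the pain measure and list its items.** Add a sensitivity analysis without overlapping content: drop item 28 if it is in the pain score, and item 59 from the general subscale.
5. **Reconcile the baseline VHNSS.** Section 10.0 uses it as a covariate; both Appendix I calendars leave it out.

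Cost: SAP wording, one extra model and slightly more reporting. The weekly pairs are already scheduled. If the VHNSS is not in fact being given at baseline, item 5 adds one questionnaire, which the instrument description puts at under 10 minutes.
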